9.3 Populations for analyses

Definitions of the analysis sets for each outcome variable are provided in Table 12.

Table 12 Summary of outcome variables and analysis populations

Outcome variable	Populations
Efficacy Data	
PFS, 6mPFS, 12mPFS	Safety analysis set
OS, 6mOS, 12mOS, 18mOS,	Safety analysis set
ORR, PROs, and symptom endpoints	Safety analysis set
DoR	Responders analysis set
TTD	Safety analysis set
PRO	Safety analysis set
Hospital resources	Safety analysis set
Demography	Safety analysis set
Biomarkers	Biomarkers Analysis Evaluable Set
Safety Data	
Exposure	Safety analysis set
AEs	Safety analysis set
Laboratory measurements	Safety analysis set
Vital Signs	Safety analysis set

AE Adverse event; XmPFS Proportion of patients alive and progression free at X months from inclusion; XmOS Proportion of patients alive X months from inclusion; ITT Intent-to-treat population; ORR Objective response rate; OS Overall survival; PFS Progression-free survival; DoR Duration of Response; TTD Time to Treatment Duration; PRO Patient-reported outcome.

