### 3.3 Responders analysis set

Responders analysis set will include the subset of patients, within the Safety Analysis Set who are evaluable for response analysis and who achieve an objective response.

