#### Endpoints analyzed:

- Progression-free survival (PFS): This analysis will be performed for the Intention-to-Treat population (ITT). PFS is defined as the time from the first date of treatment until the date of objective disease progression or death (by any cause in the absence of progression) regardless of whether the patient withdraws from IP or receives another anticancer therapy prior to progression.

**PFS (days)** = Date of event or Censor date – treatment start date +1

Patients who have not progressed or died at the time of analysis will be censored at the time of the latest date of assessment from their last evaluable assessment. However, if the patient progresses or dies after 2 or more missed visits, the patient will be censored at the time of the latest evaluable assessment prior to the 2 missed visits. If the patient has no evaluable visits or does not have baseline data, he/she will be censored at Day 1 unless he/she dies within 2 visits of baseline, in which case the date of death is the event date.

The PFS analysis will be based on the programmatically derived RECIST 1.1 using the Investigator tumor assessments. It will be analysed PFS, PFS at 6 months (6mPFS) and PFS at 12 months (12mPFS).

- Objective response rate (ORR): This outcome will be analysed for the responder's analysis set. The ORR will be based on the programmatically derived RECIST 1.1 using the investigator tumor data.
- Duration of response (DoR): This outcome will be analysed for the responder's analysis set. DoR is defined as the time from the date of first documented response per RECIST1.1 until the first date of documented progression per RECIST1.1 or death in the absence of disease progression.

DoR (days) = Date of PFS event or censoring – Date of first response +1

The end of response should coincide with the date of progression or death from any cause used for the PFS endpoint. If a patient does not progress following a response, then the patients' DoR will be censored at the PFS censoring time. DoR will not be defined for those patients who do not have a documented response. It will be analysed DoR and DoR at 1 year (DoR12)

- Overall survival (OS): This analysis will be performed for the Intention-to-Treat population (ITT). OS is defined as the time from the first date of treatment until death due to any cause.

OS (days) = Death date or Censor date - treatment start date +1

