## **5. ANALYSIS METHODS**

Descriptive statistics will be used for all variables, as appropriate. Continuous variables will be summarized by the number of observations, mean, standard deviation, median, quartiles (Q1 and Q3), minimum, and maximum. Categorical variables will be summarized by frequency counts and percentages for each category. The number of missing data will be provided for every analysed variable.

Missing values will not be considered for calculating percentages or any other descriptive, meaning that only valid values will be presented. No use of any method for the handling of missing data is foreseen.

For patients excluded from the statistical analyses, descriptive of the reasons for non-evaluability will be provided.

The software package SAS version 9.4 will be used for data analysis.

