#### Endpoints analyzed:

- Progression-free survival (PFS): The PFS analysis will be based on the programmatically derived RECIST 1.1 using the Investigator tumor assessments. The analysis will be performed using Kaplan Meier plots. Summaries of the number and percentage of patients experiencing a PFS event will be provided along with median PFS and its 95% confidence interval. In addition, the proportion of patients who are progression-free at 6 (PFS 6) and 12 (PFS 12) months will be presented.

A subgroup analysis may be conducted comparing PFS in the following subgroups, assuming sufficient sample size per subgroup: platinum therapy receiving (carboplatin or cisplatin), age ( $\geq 65$ ,  $< 65$ ), gender, performance status, smoking status, CNS metastasis at baseline (Yes/No) and number of chemotherapy cycles (5 or 6 cycles vs 4 or less cycles)

For each subgroup, the HR and 95% CI will be calculated by Cox regression and a log-rank test will be provided.

- Objective response rate (ORR): The ORR will be based on the programmatically derived RECIST 1.1 using the investigator tumor data. Summaries will be produced that present the number and percentage of patients with a tumor response (CR/PR). 95% CI will also be presented.

A subgroup analysis may be conducted comparing ORR in the following subgroups, assuming sufficient sample size per subgroup: platinum therapy receiving (carboplatin or cisplatin), age ( $\geq 65$ ,  $< 65$ ), gender, performance status, smoking status, CNS metastasis at baseline (Yes/No) and number of chemotherapy cycles (5 or 6 cycles vs 4 or less cycles). Results will be compared using Chi-Squared test.

- Duration of response (DoR): DoR will be analyzed using the investigator tumor data in responding patients. Descriptive data will be provided for the DoR in responding patients (continuous data), including the associated Kaplan-Meier curves. In addition, the DoR at 1 year (DoR 12) will be analyzed.

A subgroup analysis may be conducted comparing DoR in the following subgroups, assuming sufficient sample size per subgroup: platinum therapy receiving (carboplatin

or cisplatin), age ( $\geq 65$ ,  $< 65$ ), gender, performance status, smoking status, CNS metastasis at baseline (Yes/No) and number of chemotherapy cycles (5 or 6 cycles vs 4 or less cycles)

For each subgroup, the HR and 95% CI will be calculated by Cox regression and a log-rank test will be provided.

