## **6.2 Handling of missing data**

Missing values will not be considered for calculating percentages or any other descriptives, meaning that only valid values will be presented. The number of missing data will be provided for every analysed variable. No use of any method or imputation of data for the handling of missing data is foreseen.

For the questionnaires EORTC QLQ-C30, EORTC QLQ-LC13 and PRO-CTCAE, for each subscale, if < 50% of the subscale items are missing, then the subscale score will be divided by the number of non missing items and multiplied by the total number of items on the subscales. If at least 50% of the items are missing, then that subscale will be treated as missing. Missing single items are treated as missing. The reason for any missing questionnaire will be identified and recorded. If there is evidence that the missing data are systematic, missing values will be handled to ensure that any possible bias is minimized.

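### The SAP's valid-values-only rule makes no exception for ORR, so treated patients with no evaluable post-baseline scan can drop out of the denominator instead of counting as non-responders

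*SAP*

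**What the plan says.** The general rule is in SAP section 5: "Missing values will not be considered for calculating percentages or any other descriptive, meaning that only valid values will be presented". SAP 6.2 repeats it and adds: "No use of any method or imputation of data for the handling of missing data is foreseen". Section 5 also contains a partial safeguard. The number of missing values is to be given for every analysed variable, and "For patients excluded from the statistical analyses, descriptive of the reasons for non-evaluability will be provided".

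On ORR itself:

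- SAP 4.2.2.1: "Objective response rate (ORR): This outcome will be analysed for the responder's analysis set". SAP 3.3 restricts that set to treated patients "who are evaluable for response analysis and who achieve an objective response".
- SAP 5.2.1 asks for the count and percentage of patients with CR or PR and a 95% CI, without naming a denominator. It also allows chi-squared comparisons of ORR between subgroups, including performance status.
- The populations table in Protocol 9.3 (headed Table 12 there) puts the row "ORR, PROs, and symptom endpoints" in the Safety analysis set. Protocol 9.3.1 defines that set as all included patients who received at least one dose.

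Scans follow local practice at intervals of no more than 12 weeks, with a recommendation of about week 9 during chemotherapy (Protocol Table 1 and 4.1). Appendix E of the protocol lists not evaluable (NE) among the overall visit responses.

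**The concern.** A patient with no post-baseline scan has no RECIST response from which a best response can be derived. The only written rule on missing data takes missing values out of percentages and rules out imputation, so a programmer who counts that patient as a non-responder has no text to rely on. The SAP did foresee such patients for PFS: SAP 4.2.2.1 censors a patient with no evaluable visits at Day 1, with an exception for early death. ORR has no counterpart.

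The exclusion would probably be related to outcome. With the first scan recommended near week 9 and permitted up to week 12, patients without one are likely to include early deaths and early withdrawals. The percentage would then describe response among patients who reached a scan, not among patients treated. The study may enrol up to 30% of patients with performance status 2 (Protocol 5.1). If the unassessed share is higher in that group, the comparison of ORR by performance status is affected as well as the overall figure.

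**Working it through.** **The plan's own figure.** The documents give no planning value for ORR. The nearest reproducible figure is the exact 95% interval at N = 85 in Protocol 9.2. Clopper-Pearson with 51/85 gives 48.8 to 70.5, and with 60/85 gives 59.7 to 80.0. Both match the printed limits for 60% and 70%. The half-widths are about 10.8 and 10.1 points.

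**Step 1: ORR as SAP 4.2.2.1 now reads.** In the responders set every patient is a responder, so ORR = r/r = 100% for any r, and the missing-data rule has no effect. That assignment contradicts Protocol 9.3 and has to be corrected first.

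**Step 2: ORR in the Safety analysis set under the valid-values rule.** Let N be the treated patients, r the responders and m the patients with no evaluable post-baseline scan. None of the m can be a documented responder, so r does not change:

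reported ORR = r/(N − m) = (r/N) × 1/(1 − m/N).

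The factor exceeds 1 whenever m > 0, so the shift can only be upward. The relative increase passes 10% once m/N exceeds 1 − 1/1.1 = 9.1%.

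**Step 3: size.** N = 85 is the planned sample. Both r and m are assumptions; the introduction to the protocol cites response rates of up to 70% for chemotherapy.

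| Assumed responders | All treated | m = 4 | m = 9 | m = 13 |
|---|---|---|---|---|
| 51 | 60.0% | 63.0% | 67.1% | 70.8% |
| 55 | 64.7% | 67.9% | 72.4% | 76.4% |
| 60 | 70.6% | 74.1% | 78.9% | 83.3% |

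With 55 responders and m = 5, 55/80 = 68.8%, about 4 points above 64.7%. With m = 9, 55/76 = 72.4%, which is 7.7 points above. The exact interval moves from 53.6–74.8 to 60.9–82.0.

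**Step 4: how large m might be.** The documents do not say. A crude guide is exponential survival with the 13.0-month median OS quoted in Protocol 2.3.1.2: P(death by week w) = 1 − 2^(−t/13.0), with t = 7w/30.44 months. This gives 10.4% by week 9 (8.9 of 85) and 13.7% by week 12 (11.6 of 85). It probably overstates m. At 18 months the same model predicts 2^(−18/13.0) = 38.3% alive, against the 33.9% cited in Protocol 2.3.3. That points to a hazard that rises with time and so to fewer early deaths than the model gives. The 12-week life-expectancy criterion and unscheduled scans also lower m; withdrawals raise it.

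**Step 5: subgroup illustration (all counts assumed).** Take PS 2 with 15/25 = 60.0% and PS 0–1 with 40/60 = 66.7%. With 4 and 2 patients unassessed, the reported figures become 15/21 = 71.4% and 40/58 = 69.0%, and the ordering reverses.

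**The case against.** A reader might infer that the SAP in terms removes early deaths and clinical deteriorations from ORR, and that the reported ORR is therefore inflated by a known amount. The documents do not support that much, for five reasons.

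- **Removal is an inference.** The SAP never says that a patient without a scan is a missing value for ORR. NE is a recorded visit category, and the SAP 5.2.1 statistic can be read as a patient-level yes/no. This stands: exclusion is the natural reading but not the only one. NE does not fully answer the point, because it classifies a visit, and a patient who dies before any follow-up scan has no visit to classify.
- **The bias is not active in the SAP as written.** The responders set makes ORR 100% first. This stands. The two corrections belong together, because fixing only the population leaves the second defect in place.
- **Clinical deterioration does not by itself stop scanning.** The protocol continues tumour assessments after discontinuation for toxicity or symptomatic deterioration (1.2, 6.1.3). This stands, so only early deaths and withdrawals are named here as likely contributors. Scanning follows local practice, so administrative gaps are possible too.
- **Missing counts and reasons are to be reported.** A reader could largely rebuild the all-treated figure. The headline percentage, its interval and any chi-squared tests would still use the reduced denominator.
- **The size is assumed.** At m = 5 the shift of about 4 points is well inside the roughly ±10-point interval at N = 85. That is a fair limit on importance. It is not a defence of the rule, since the shift has one direction.

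**Conclusion.** Wrong as written, with moderate severity. The SAP has a stated missing-data rule that applies to every percentage, no exception for ORR, and no non-responder convention in either document. Applied to ORR in the Safety analysis set, the rule can only raise the estimate, by 1/(1 − m/N). With an assumed 55 of 85 responders, that is about 4 points at m = 5 and 7.7 points at m = 9.

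The direction rests only on the fact that a patient without an evaluable post-baseline scan cannot be a documented responder. The size rests on assumed r and m, and the documents supply neither. The conclusion also assumes that patients without a scan would be treated as missing, and that ORR has been moved to the population the protocol names.

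ORR is one of several secondary descriptive endpoints in a single-arm safety study with no formal hypothesis. This point does not touch the primary safety endpoints, and the subgroup comparisons are optional and depend on sample size.

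**What to change.** Amend four places together, so that the SAP does not end up naming two ORR denominators:

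- **SAP 4.2.2.1:** replace the responders set with the Safety analysis set for ORR. DoR stays in the responders set.
- **SAP 5.2.1:** state that the ORR denominator is all patients in the Safety analysis set, and that patients with only NE assessments or with no post-baseline assessment, including those who die or withdraw before the first scan, count as non-responders. Apply the same denominator in the ORR subgroup tables.
- **SAP 5 and 6.2:** state that the valid-values rule does not apply to ORR or its subgroup tables.

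The number of patients without an evaluable assessment, with reasons, should appear beside ORR; section 5 already provides most of this. An evaluable-only ORR may be kept as a labelled sensitivity analysis.

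The cost is a few sentences and a somewhat less favourable ORR than the valid-values rule would give. No new data are needed, and the SAP then agrees with Protocol 9.3.

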## 5.1 Primary outcome

**Primary objective:** To describe safety profile of durvalumab in combination with platinum–etoposide as first-line treatment for patients with ES-SCLC.

### Endpoints analyzed:

- Incidence of grade  $\geq 3$  AEs
- Incidence of imAE.

Safety data will be summarized descriptively overall, by seriousness, by causality, and by maximum NCI CTCAE Grade. The exact 95% CIs around the incidence of Grade 3 and Grade 4 AEs will be reported. All outputs will be summarized for the Safety analysis set.

A subgroup analysis may be conducted in the following subgroups, assuming sufficient sample size per subgroup: platinum therapy receiving (carboplatin or cisplatin), age, gender, performance status, smoking status and CNS metastasis at baseline (Yes/No).

For this aims, the following summaries of AEs will be provided:

- Number and percentage of patients with AEs in total and by causality and severity
- Number and proportion of patients with Grade 3 and Grade 4 AEs in total and by causality
- Number and proportion of patients with SAEs in total and by causality
- Number and proportion of patients with AEs leading to death
- Number and proportion of patients with AEs leading to treatment interruption and/or discontinuation
- Number and proportion of patients with AESI, by predefined type (or newly defined by this study) in total and by seriousness, severity and causality, including immune relatedness
- Number and proportion of patients who received steroids, immunosuppressants, and/or hormone replacement therapy to manage AESIs
- Time from start of durvalumab to the onset of an AESI predefined type, all interventions of AESIs by type of intervention (including intervention with steroids, immunosuppressants, and/or hormone replacement therapy), and time from onset of an AESI type to resolution.
- Duration of the intervention with steroids, immunosuppressants, and/or hormone replacement therapy until the resolution of AESI.
- Number and proportion of patients with imAEs. The imAEs will be assessed as a subset of AESIs. An imAE is defined as an AESI that is associated with drug exposure and is consistent with an immune-mediated MOA and where there is no clear alternate etiology.
- Listing of SAEs per patient, including the following variables:
  - Patient ID
  - AE number
  - AE description
  - PT Term
  - Grade NCI-CTCAE v5.0 (1-5)
  - Onset date (DD-MMM-YYYY)

- End date (DD-MMM-YYYY)
- Ongoing (Yes; No)
- Outcome
- Seriousness criteria
- AESI (Yes; No)
- Relationship
- Action taken

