9.2 Sample size determination

This is a safety study, and given the real-world setting, there is no formal predefined statistical hypothesis and no formal sample size calculation will be done.

A convenience sample size of approximately 85 patients was estimated based on the expected accrual potential during 6 months in 30 sites, although the recruitment duration may be reduced or extended, until P&R approval of durvalumab in Spain for ES-SCLC based on CASPIAN results. Therefore the number of patients recruited could be higher than 85 patients. A maximum of 30% of recruited patients will have ECOG performance status of 2 at baseline.

Assuming a sample size up to 85 and a 70% incidence of AE of CTCAE grade ≥ 3 , the estimated precision will be no wider than 10% based on exact method (Clopper-Pearson). In addition, assuming a 20% incidence of imAE, the estimated precision will be no wider than 9% using the same method. An illustration of the precision around the varying incidences of AE for the patients enrolled is provided in Table 12.

Table 11. Precision around varying incidence of AE

Precision of estimates of G3+ or imAE for varying Sample Sizes using Exact Binomial 95% CI				
Sample size	True rate of Grade 3+ AE or imAE (%) and 95% CI			
	20%	25%	60%	70%
85	$\pm 9.0\%$ 12.1-30.1	$\pm 9.7\%$ 16-35.3	10.9% 48.8-70.5	$\pm 10.0\%$ 59.7-80.0

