9.5.1 Analysis of the primary variables

Safety data will be summarized descriptively overall, by seriousness, by causality, and by maximum NCI CTCAE Grade. The exact 95% CIs around the incidence of Grade 3 and Grade 4 PRAEs will be reported. All outputs will be summarized for the safety analysis test.

A subgroup analysis may be conducted in the following subgroups, assuming sufficient sample size per subgroup: platinum therapy receiving (carboplatin or cisplatin), age, gender, performance status, smoking status and CNS metastasis at baseline (Y/N).

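### The only exact 95% CI in SAP 5.1 is for Grade 3 and Grade 4 AEs, not the primary endpoint of Grade ≥3 AEs, and no CI is named for the other primary endpoint, imAE

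*SAP*

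**What the plan says.** SAP 4.2.1 and 5.1 list the same two primary endpoints: incidence of Grade ≥3 AEs and incidence of imAE, in the Safety analysis set, treatment-emergent events only. The analysis text in SAP 5.1 then says "The exact 95% CIs around the incidence of Grade 3 and Grade 4 AEs will be reported". The matching item in its list of summaries is "Number and proportion of patients with Grade 3 and Grade 4 AEs in total and by causality". AEs leading to death are a separate item. For the second endpoint the item is "Number and proportion of patients with imAEs", with no interval. Safety data are also to be summarised by maximum CTCAE grade.

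The protocol has the same limit. Section 9.4 counts Grade 3 and Grade 4 AEs only, and Section 9.5.1 says "The exact 95% CIs around the incidence of Grade 3 and Grade 4 PRAEs will be reported". The term PRAE is in neither abbreviation list.

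Protocol 9.2 uses the endpoints as defined. For Grade ≥3 AEs at a 70% rate it says "the estimated precision will be no wider than 10% based on exact method (Clopper-Pearson"), and for imAE "assuming a 20% incidence of imAE, the estimated precision will be no wider than 9% using the same method". Its table is titled "Precision of estimates of G3+ or imAE for varying Sample Sizes using Exact Binomial 95% CI". The protocol synopsis also promises 95% CIs for event rates in general, without naming an endpoint or a method, and the SAP does not carry that sentence over.

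**The concern.** Grade ≥3 means Grades 3, 4 and 5. A rate built on Grades 3 and 4 can leave out a patient whose only Grade ≥3 event was fatal, so it can equal or understate the primary endpoint but cannot exceed it. A programmer who follows SAP 5.1 literally would attach the exact interval to that other quantity, would produce no combined Grade ≥3 line, and would give imAE no interval.

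The study has no hypothesis, so the estimate and its interval are the whole primary result. The SAP does name 95% CIs for secondary results (ORR, median PFS, median OS). SAP 7 schedules the Section 5.1 outputs for October 2021, so the wording governs that output as well as the final one.

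**Working it through.** **Inputs.** n = 85, an assumed 70% rate of Grade ≥3 AEs and an assumed 20% rate of imAE (protocol 9.2). Fatal AEs in 5% of patients on durvalumab plus chemotherapy, and Grade 3 or 4 AEs in 61.5% (protocol 2.3.2.2, from the cited phase III trial). Carrying these two rates over to this study is an assumption.

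**Step 1: reproduce the plan's table.** For x events in n patients, the exact 95% limits are the 2.5% quantile of Beta(x, n−x+1) and the 97.5% quantile of Beta(x+1, n−x).

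| Row | x/85 | Exact 95% CI | Half-width | Plan |
|---|---|---|---|---|
| 20% | 17 | 12.1 to 30.1 | 9.0 | 12.1 to 30.1, 9.0 |
| 25% | 21 | 16.0 to 35.3 | 9.6 | 16 to 35.3, 9.7 |
| 60% | 51 | 48.8 to 70.5 | 10.8 | 48.8 to 70.5, 10.9 |
| 70% | 60 | 59.7 to 80.0 | 10.1 | 59.7 to 80.0, 10.0 |

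All limits match, and the half-widths agree within about 0.1 point. The planned precision therefore refers to exact intervals for Grade ≥3 AEs and imAE, which SAP 5.1 does not name.

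**Step 2: size of the gap, pooled reading.** Read the SAP sentence as one pooled rate of patients with any Grade 3 or 4 AE. Start from a true Grade ≥3 count of 60/85 = 70.6%. Fatal AEs: 0.05 × 85 = 4.25, about 4 patients.

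- Every fatal case also had a Grade 3 or 4 AE: the count stays at 60, gap 0.
- Fatal and Grade 3 or 4 events independent: solve 1 − (1 − q)(1 − 0.05) = 0.706, giving q = 0.690. The gap is about 1.5 points, or 1.3 patients. The nearest whole count is 59/85 = 69.4% (58.5 to 79.0).
- No fatal case had a Grade 3 or 4 AE: 60 − 4 = 56, and 56/85 = 65.9% (54.8 to 75.8), gap 70.6 − 65.9 = 4.7 points.

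Starting from the other end gives the same maximum: 0.615 × 85 = 52.3, so 52/85 = 61.2% (50.0 to 71.6) for Grade 3 or 4, and Grade ≥3 of up to 56/85 = 65.9%, again 4.7 points.

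**Step 3: other readings.** If patients are classified by maximum grade, every patient with a fatal AE falls outside Grades 3 and 4. The zero end then disappears, and the gap is the fatal share, 4/85 = 4.7 points. If separate intervals for Grade 3 and for Grade 4 are meant, each covers only part of the endpoint, and the gap can be larger than any figure above.

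**Step 4: imAE.** At the planned 20%, the interval SAP 5.1 does not commit to is 17/85, 12.1 to 30.1.

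**The case against.** The best defence is that little is lost. Both endpoints are named with their analysis set, SAP 5 commits to counts and percentages for categorical variables, and imAE has an explicit number and proportion. The maximum-grade summary lets a reader rebuild the Grade ≥3 count, deaths are shown separately, and either exact interval can be computed from the count and denominator. The synopsis sentence on 95% CIs, read with protocol 9.2, shows what was intended. Grade 3 or 4 with deaths alongside is also how the synopsis lists its AE summaries and how the cited trial is quoted. Most patients are expected to have a Grade 3 or 4 AE anyway, so the 4.7-point end needs an unlikely pattern under the pooled reading.

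All of this stands as to weight. It does not supply the missing commitment: the synopsis names neither endpoint nor method, protocol 9.2 is not a reporting instruction, and the one interval that is specified belongs to another quantity.

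A reader might infer three stronger things that the documents do not support:

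- **That the sample size rests on the imAE interval.** Protocol 9.2 describes a convenience sample set by expected accrual, with no formal calculation, and offers the precision table as an illustration.
- **That fatal events go unreported.** They have their own line.
- **That PRAEs is simply a slip for AEs.** The SAP's wording suggests it, but the term is undefined and only the authors can say.

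**Conclusion.** The point holds as a mis-specified primary interval. SAP 5.1 and protocol 9.5.1 attach the exact CI to a quantity that is not the stated Grade ≥3 endpoint, provide no Grade ≥3 count line, and name no interval for imAE. It would be too much to say that the primary estimates are undefined, since the endpoints and population are clear; what is missing is the matching interval and the explicit Grade ≥3 line.

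The likely numerical effect is small: 0 to 4.7 points, about 1.5 under independence, against a planned half-width of about 10. That range assumes the pooled any-occurrence reading and fatal AEs in about 5% of patients. It is not a complete range, because the sentence permits the other readings in step 3. The analyses are descriptive, so no decision rule is affected. It should still be corrected, because the primary result of a safety study should carry its own interval.

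Two neighbouring wording questions are separate and add nothing to this point: whether the primary objective mentions maintenance treatment, and whether AEs after further anticancer therapy are left out of the tables (protocol 9.5.2.1).

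**What to change.** In SAP 5.1 and protocol 9.5.1, replace the CI sentence with: *The number, percentage and exact (Clopper-Pearson) 95% CI will be reported for (i) patients with any Grade ≥3 (3, 4 or 5) treatment-emergent AE and (ii) patients with any treatment-emergent imAE.*

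Add the Grade ≥3 count to the lists in SAP 5.1 and protocol 9.4. Keep Grade 3 or 4 as a supplementary summary, so that the result can still be set beside the Grade 3 or 4 rate quoted from the cited trial. Ask the protocol authors to confirm or correct PRAEs.

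The cost is one replaced sentence in each document and one added line in each count list. No new data are needed, because CTCAE grade is already collected and imAEs are already to be summarised. The trade-off is that Grade ≥3 and Grade 3 or 4 will appear side by side and must be clearly labelled.
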